 - 1.1 Study the course of COVID-19 disease i.e. its symptoms, duration, progression in pregnant women
 - 1.2 Study the pregnancy, postnatal and neonatal effect of COVID-19 disease

Objective justification

The in-utero exposure of acute viral infection in some instances is proven to have short- and long-term neonatal effect during the postnatal and childhood period and the Zika virus, measles, mumps and rubella are few examples. COVID-19 is caused by a novel coronavirus strain of unknown consequences. The main purpose of this registry is to collect a baseline data and help establishing future studies and hypothesis generation.

In addition, we will be exploring the psychological impact of COVID-19 on women during the pregnancy and postnatal period. Stress and anxiety level are increased with potential adverse pregnancy and/or neonatal outcomes especially during infectious disease outbreak. In fact, COVID-19 is associated with adverse maternal and neonatal outcomes resulting in increased level of stress and anxiety. In addition, women during the pregnancy, peripartum, and postpartum period are at increased risk of depression. A risk that has been aggravated by social and physical isolation. Indeed, the social and physical isolation, a critically needed measure to stop the virus transmission, resulted in increased stress and depression level and adversely affecting the mental and physical health of both the mother and the baby.

5. Indicate if this is a retrospective data review

- **Retrospective Chart/data Review**
- **Provide the date range of the chart review**

6. Study Methodology

This is a nationwide prospective observational registry linked with PAN-COVID UK register of pregnant women with suspected and/or confirmed diagnosis of COVID-19 infection. The enrollment period for this registry is 2 years e.g. May 1, 2020 to May 1st, 2022. Case reports or cases diagnosed ever since 27th Feb will also be included. The authors of published case reports will be contacted for permission. This registry will open for enrollment after IRB/MRC approval. Understanding the effect of COVID-19 infection on pregnancy and its outcome is imperative to help the patients and healthcare providers understand the impact of the disease on the pregnant women and their offspring. There is no intervention planned in this study, therefore, there is a minimal risk associated with this study.

Data collection:

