Objective 1: To form a disease registry **linked with other national data sources** for women with suspected COVID-19 or confirmed SARS-CoV-2 in pregnancy and their neonates.

Objective 1.1: Study the course of COVID-19 disease i.e. its symptoms, duration, progression in pregnant women

Objective 1.2: Study the pregnancy and neonatal effect of COVID-19 disease

We will collect information about patient demographic, co-morbidities, clinicopathological information, COVID-19 disease sign, symptoms and its treatment, pregnancy and neonatal outcomes, and women mental health during pregnancy and postnatal period. Regarding pregnancy outcomes, our study will focus on miscarriage, fetal growth restriction and stillbirth, pre-term delivery and vertical transmission and will include fields on ultrasound diagnosis and neonatal care (for details refer to appendix 1, 2 and 3). The woman and her neonate(s) will be followed for 1 year postnatally. Regarding the neonatal outcomes, outlined in the neonatal outcome data collection sheet, includes birth weight, congenital malformations, APGAR score, Breastfeeding, COVID-19 status, respiratory symptoms, neonatal status, and discharge status.

Baseline characteristic and initial assessment will be done during the hospital admission up on COVID-19 diagnosis. Apart from that, there are 7-10 expected follow up telephone calls or online forms to be sent to the patient. The schedule and timeline of data/biospecimen collection are described in table 1.

Data Collection Form or Questionnaire	Baseline	Weekly for 4 weeks	2 nd Trimester (GA 24 weeks)	3 rd Trimester (GA 34 weeks)	GA 36 weeks	GA 38 weeks	6 weeks postpartum	6 Months	12 Months
Demographics, Health History and COVID-19 Questions	X								
COVID-19 Symptoms Follow-up		X	X	X			X	X	X
Pregnancy Status/Outcomes		X	X	X	X	X	X		
Depression and Anxiety*	X		X	X			X	X	X
Neonatal/Infant Outcomes							X	X	X

*Generalized Anxiety Disorder 7-item (GAD-7) scale and Edinburgh Postnatal Depression Scale (EPDS)

7. Study Population and Study Setting/ Location

We will include all pregnant patients with suspected or confirmed COVID-19 infection at all HMC facilities including WWRC, CH, AKH, AWH and its associated quarantine sites and their offspring's. The inclusion criteria are:

1. pregnant woman with suspected or confirmed SARS-CoV-2 infection
2. postpartum women who delivered during the last six weeks and
3. neonate(s) of women included in the registry.

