We will also contact corresponding authors of case reports of women with COVID-19 from February 2020 for their written consent, by email, for inclusion of the data from these reports in the PAN-COVID register.

Sample size calculation:

Based on a recently published study, 15% of pregnant women were SARS-CoV-2 positive. Out of which only 12% (1.9% of total study patients) were symptomatic. The total number of deliveries per year in Qatar is between 19000 – 21000 deliveries (1650 patients/month). Diagnosis of COVID-19 in Qatar is based on selective criteria i.e. presenting with symptoms, recent travel to endemic area or contact with a confirmed case. However, all women undergoing cesarean section are screened. Therefore and based on 95% CI and 0.05 margin of error, we anticipate a total 170 - 200 case per month.

8. Study procedures

Study Duration and Timelines

This registry is expected to enroll patients for 2 years and follow them up to 1 year postnatally i.e. the registry duration will approximately last for 4 years.

Study timeline:

Patient enrollment: 2 years

Data collection and curation: 4 years

Study visit numbers: 7-10 visits ([see details below](#)); Initial patient visit is expected to last for 30 minutes.

1. [baseline,](#)
2. [weekly for 4 weeks,](#)
3. [At 24 – 34 – 36 – 38 weeks of gestation \(provided that baseline and the 4 weekly follow up occurred earlier\),](#)
4. [At 6 weeks, 6 and 12 months postpartum \(for both mother and the baby\)](#)

[Further to that, the first visit “baseline” will be collected by the primary physician who is taking care of the participating patient. All subsequent visits will be over the phone with mother.](#) Telephone calls for follow up visit are expected to last 15 – 30 minutes.

Data analysis: interim and final

Final report: 2 months

Study procedure:

Suspected patient or patients with positive COVID results will be identified through Cerner. Patients will then be contacted through the primary physician to explain the study and obtain consent forms once accepted. The primary physician will then collect demographic and baseline data after obtaining patient consent (appendix 1 & 2). Apart from the initial visit, there is no anticipated future study visits. Data collection will be either through the phone or using a self-administered survey that will be sent through SMS.

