The maximum follow-up period is 2 years. Based on the gestational age at time of enrolment might vary e.g. if the patient was enrolled early in pregnancy e.g. during the first trimester, the enrollment period will be for 2 years whilst patient who is enrolled in third trimester will be enrolled for less than 2 years.

During the follow up, patient will be contacted over the phone.

Further, we aim to collect data about psychological status i.e. depression and anxiety disorders using the depression Edinburgh Postnatal Depression Scale (EDPS) and the Generalized Anxiety Disorder 7 (GAD-7) surveys. Both surveys, the EDPS and GAD-7, are self-administered surveys that will be sent through an SMS link to the subject. In case patient was identified as having depression or anxiety disorder, the patient will be referred to contact the national mental health helpline at [name]. In case the study team is concerned about the mental health of the subject a direct referral will be sent through Cerner and psychiatrist will be consulted.

Informed Consent

a) *How people will be **NOTIFIED OR APPROACHED** to consider being a research subject in this study?*

Patient will be notified through:

1. Advertisements such as hospital posters and social media. In this case, filling the study online form will be considered as a patient consent.
2. Referral through the primary physician. In this case, the primary physician will explain the study to the patient and document her willingness to participate in Cerner.

b) *Describe the **CONSENT PROCESS** procedures (When, Where, How, by Whom).*

When an eligible patient is referred by her primary physician, a study coordinator will follow-up by phone to explain the study and obtain a verbal consent to release medical information. In case of self-referral, through filling the online form or calling the study coordinator, a study coordinator will follow with a phone call to explain the study and obtain a verbal informed consent.

c) *Describe **HOW LONG** potential participants will have to decide on participation.*

The patient will be given a 24-hour period to decide.

d) *Describe how subjects will be **SCREENED FOR ELIGIBILITY** for the study.*

Patients will be screened based on a confirmatory laboratory result of a positive SARS-CoV-2 PCR results.

e) *Describe how subjects will be **ENROLLED** into the research study below.*

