Once the laboratory result is confirmed and verbal consent is obtained, patient details will be entered into the online study database and given a study number.

Risk

The is a prospective observational registry. There minimal risk of breach of patient confidentiality. To minimize this risk, data will be entered into an electronic registry software. The software will be secured with username and password and only accessible by the study investigators for data entry. Data extraction will only be accessible to study PIs and co-PIs. Paper based data collection sheet will be secured in locked cabinets accessible only by study PIs and co-PIs. Only de-identified data will be shared amongst investigators. If a breach in confidentiality occurs, the IRB will be notified immediately. Consent form containing the linking information between collected data and patient's identifiable information will be stored in a locked cabinet and/or password locked computer. Information on the password protected computer database will only be accessed by the investigators. Furthermore, the PI's office will remain locked. All study documentation will be stored according to the MRC guidelines

Bio-Specimens & Sample Collection

NA

Outcomes

We believe the results of this study will generate robust data. Prevalence of SARS-CoV-19 infection in pregnancy. Percentage and distribution of COVID-19 presenting sign and symptoms. Percentage of adverse pregnancy and neonatal outcomes. Description of mental status of pregnant women affected by COVID-19 infections.

Data Collection, Management & Confidentiality

a) Indicate below HOW study data will be collected for the proposed research.

Study Forms Study Database Study Web-Based/App Other

Please detail how study data will be coded:

Once informed consent is obtained, patient will be given study number and entered in the registry system. Data will be stored registry database/web-portal password protected on Cerner. Only study investigators have access for data entry. For follow up purposes, study investigators will have access to the identifiable information during the data collection period. No individual identity will be disclosed in results and publications.

b) Describe below WHERE and HOW the study data is physically stored.

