Data collection/entry: HMC physicians will be eligible to enter patient initial assessment form. Follow up data study investigators and research coordinators will have access to enter patient data into the database.

Data extraction for audit, analysis, report and request of collaboration:

Data extraction access will be granted to specified personnel designated by the register steering committee.

e) Describe below HOW the study data is accessed.

Level access will be employed from HMC Cerner team. Study data will be accessed using a dedicated username and password for specified members.

f) Will subject identifiers be shared outside of HMC? If YES describe below WHOM the study data is shared

No, only deidentified data will be shared.

Subject Withdrawal/ Withdrawal of Consent

In case patient wish to be withdrawn from the study, no further contact will be made. However, collected information up to the point of withdrawal will be included in the analysis. Subjects withdraw from the study will be asked whether they are willing to allow ongoing data collection and his response will be recorded.

9. Statistical Consideration and Data Analysis

Descriptive data: Numerical data will be presented as mean and standard deviation where normally distributed or median and range where it's not normally distributed. Categorical data

will be presented as frequency and percentages. Prevalence of COVID-19 will be calculated as total number of patients who were positive over total number deliveries in the same month. Inferential analysis will be used to assess association and tests will be selected according to suitability.

10. Adverse Event Reporting

This is an observation study. There are no anticipated adverse events.

11. Ethical Consideration.

The registry will only commence after obtaining approval from IRB/HMC in accordance with good clinical practice, and MoPH regulations

12. Sponsor, Funding & Collaborator Information

MRC

13. Dissemination of Results and Publication policy

Once the project is funded, the study team will initiate monthly meetings to discuss study plans and patient recruitment. Team leaders will also meet monthly to share study updates. Furthermore, the study results will be shared among peers in the department through presentation of study findings. Finally, once the study is completed, we aim to present our findings at the Hamad Medical Corporation Annual Research Day, local and international conferences and in peer-reviewed journals.

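### Section 9's prevalence (positive patients over the month's deliveries) is not prevalence of infection in pregnancy: testing is selective and the numerator is not fully specified

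*Combined protocol and SAP*

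**What the plan says.** Section 8 (Outcomes) lists "Prevalence of SARS-CoV-19 infection in pregnancy" as an outcome. The only rule for computing it is in Section 9: "Prevalence of COVID-19 will be calculated as total number of patients who were positive over total number deliveries in the same month". No confidence interval, restriction to tested women or caveat is attached.

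Four other places bear on the two counts:

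- **Who is tested.** Section 7 (Sample size calculation) says diagnosis follows selective criteria: "presenting with symptoms, recent travel to endemic area or contact with a confirmed case". The stated exception is caesarean section, where every woman is screened. The same paragraph cites a study in which 15% of pregnant women were positive and 12% of those positives (1.9% of all women studied) had symptoms.
- **Which women are in the registry.** Section 7 admits pregnant women without a gestational limit, and also "postpartum women who delivered during the last six weeks and". Section 8 foresees early entry: "if the patient was enrolled early in pregnancy e.g. during the first trimester".
- **What puts a woman in the database.** Section 8 (Informed Consent, item e): "Once the laboratory result is confirmed and verbal consent is obtained, patient details will be entered into the online study database".
- **Where.** Recruitment is "at all HMC facilities including WWRC, CH, AKH, AWH" and associated quarantine sites, whereas the only delivery total given (Section 7) is for all of Qatar.

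**The concern.** A prevalence needs a numerator drawn from its denominator, and infection status known for everyone in that denominator or for a representative sample of them. The Section 9 ratio does not secure either condition.

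The first problem is testing. A woman delivering vaginally with no symptoms, travel or contact is not tested under the criteria described, yet she is counted among the deliveries and so is treated as uninfected. This remains however the numerator is read.

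The second is matching. Section 9 does not limit the positives to women delivering that month. A woman positive in her first trimester could count in the numerator although she is not among that month's deliveries. Nor does Section 9 say whether the deliveries are those of HMC sites or of Qatar, or whether the positives are all those identified or only consenting women.

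At stake is a figure that would be published under the name of prevalence while depending on who was tested and who was counted.

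**Working it through.** **The plan's own figures.** Section 9 gives no expected prevalence to reproduce. In Section 7, 15% × 12% = 1.8%, against the stated 1.9%, which is consistent with rounding; 1.9/15 = 12.7% is used below. The 170–200 cases per month in Section 7 are not used. They are close to a precision sample size, 1.96² × 0.15 × 0.85 / 0.05² = 196 (about 175 with a finite-population correction for 1,650 deliveries), whereas 15% of 1,650 is 247.5 cases. No prevalence can be inferred from them.

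**Reading A: positives limited to women delivering that month.**

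From the documents:
- p = 0.15, taken as the true prevalence for illustration
- f = 1.9/15 = 0.127, the symptomatic share of positives

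Assumed, because the documents do not give them:
- c = 0.20–0.40, the caesarean share of deliveries
- t = 0–0.20, the share of other infections found through contact or travel testing
- every symptomatic woman is tested, every test on an infected woman is positive, and infection status is taken at delivery

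Ratio = p × [c + (1 − c) × (f + (1 − f) × t)]

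| c | t | Calculation | Ratio |
|---|---|---|---|
| 0.20 | 0 | 0.15 × (0.20 + 0.80 × 0.127) | 4.5% |
| 0.40 | 0 | 0.15 × (0.40 + 0.60 × 0.127) | 7.1% |
| 0.20 | 0.20 | 0.15 × (0.20 + 0.80 × 0.301) | 6.6% |
| 0.40 | 0.20 | 0.15 × (0.40 + 0.60 × 0.301) | 8.7% |

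Here 0.301 = 0.127 + 0.873 × 0.20. A true 15% reads about 4.5–9%. If only half of symptomatic infections were detected (f replaced by 0.063, t = 0), the range would be 3.8–6.6%.

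**Reading B: positives at any stage, over the month's deliveries.** Let R be the women at risk per monthly delivery. From recognition of pregnancy at 5–12 weeks (assumed) to 39 weeks (assumed), plus six weeks postpartum, R = (39 − 12 + 6)/4.345 = 7.6 to (39 − 5 + 6)/4.345 = 9.2. Let m be the month's count divided by the point-prevalent cases, which is unknown.

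Ratio = p × [(f + (1 − f) × t) × R × m + (1 − f) × (1 − t) × c]

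- t = 0, m = 0.5: 0.15 × (0.127 × 7.6 × 0.5 + 0.873 × 0.20) = 9.8%, up to 14.0% at R = 9.2 and c = 0.40.
- t = 0.20, m = 1: 0.15 × (0.301 × 7.6 + 0.873 × 0.80 × 0.20) = 36.4%, up to 45.8% at R = 9.2 and c = 0.40.

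The mismatch always pushes the ratio up relative to Reading A, but the net result can fall on either side of 15%. These figures show only that size and direction are not determined. They are not bounds.

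**The case against.** **The numerator is given.** A reader might infer that it is wholly undefined. The documents do not support that: Section 9 names positive patients, and Section 8 (Informed Consent, item d) ties eligibility to a positive PCR. What is missing is the stage of pregnancy, consent status and the month to which a case belongs. The fair description is under-specified.

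**The natural reading is women delivering.** Section 7 sets its 15% positivity beside monthly deliveries, so Section 9 can be read as positives among that month's deliveries. A reader might otherwise infer that the published figure will be inflated, perhaps several-fold. That holds only if all stages are counted and depends on quantities the documents do not give. But the delivering-only reading removes only the upward error; the downward error from selective testing stays.

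**Case reports.** Section 6 says "Case reports or cases diagnosed ever since 27th Feb will also be included", which might suggest that published reports enter the ratio. Section 7 asks authors for permission to include their data in the PAN-COVID register, which points away from a monthly ratio for Qatar. A short exclusion is enough.

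**This is a descriptive registry.** Prevalence is not a numbered objective in Section 4, and the stated purpose is baseline data and hypothesis generation. That limits the severity. It does not remove the point, because proportions are what a descriptive registry reports.

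**Conclusion.** The concern holds. On the plan's own account of testing, the Section 9 ratio is not prevalence of infection in pregnancy under any reading. Counting only delivering women biases it downward; counting all stages adds an upward error. The mix of sites and the consent requirement add further ambiguity. That conclusion rests on the text of Sections 7, 8 and 9 and not on the illustrative figures.

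The size cannot be determined from the documents. The 4.5–9% reading of a true 15% rests on the caesarean share, detection shares and test performance assumed above, and should be cited only as an illustration.

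This should be fixed before analysis. A reader might infer that the registry's findings in general are compromised. They are not: symptom, pregnancy, neonatal and mental-health results do not use this ratio.

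**What to change.** **1. Rename and match the counts (needed).** In Section 9 and in the Section 8 outcome, call the ratio 'detected cases per 100 deliveries' and do not report it as prevalence.

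- Numerator: women delivering at HMC sites in the month who have a positive PCR. State over what period before delivery a positive test counts.
- Denominator: all deliveries at the same sites in the same month.
- Exclude published case reports.
- State that the ratio depends on testing coverage.

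Cost: a few sentences, site delivery counts, and an aggregate Cerner count of positive women. The registry holds only consented women, so the approval must cover that count. If it is not available, use enrolled women only and label the ratio 'enrolled cases per 100 deliveries'.

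**2. Prevalence at caesarean delivery (optional).** If the aggregate counts can be obtained under the approval, report PCR-positive women over all women screened at caesarean section, same sites and months, with a 95% confidence interval and that label. The text should state three limits:

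- It does not generalise to all pregnancies.
- It may be biased upward if infection raises the chance of caesarean. With an assumed ratio of 1.25–1.5, a true 15% reads 0.1875/1.0375 = 18.1% to 0.225/1.075 = 20.9%.
- How women already known to be positive are handled. If 12.7–30% of positives (assumed) are known beforehand and left out of both counts, a true 15% reads 0.131/0.981 = 13.4% down to 0.105/0.955 = 11.0%.

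If these counts cannot be obtained, the first change is sufficient.
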